Hearing and Speech Evaluation: Hearing thresholds and speech perception performance will be measured during the baseline visit, and 1 month and 6 month follow up visits using standard, validated and standard word and sentence lists presented in quiet and in noise (AzBio Quiet, AzBio +5/+10dB; CNC 50-item list) while the patient is wearing an appropriately programmed CI alone and/or with appropriately fitted contralateral hearing aid (if this is typically worn by the patient).

5) Study Schedule:

Visit 1/Baseline:

Subjects will undergo a screening visit to determine eligibility. The screening visit may be combined with a standard of care visit for patients already being seen for cochlear implant evaluation. Each participant will sign an informed consent before committing to any study-related tests or procedures and will include the following assessments:

- Obtain and document consent from potential participant on informed consent form (ICF).
- Conduct baseline hearing threshold and speech perception testing using standard audiological procedures (e.g., AzBio Quiet, AzBio +5/+10dB; CNC 50-item list) for screening for eligibility and baseline assessment
- Obtain patient reported outcome questionnaires (SSQ-12 and CIQOL)
- Auditory training and assignment of home-based personalized, computer-based rehabilitation/practice plan
- Orientation to tDCS equipment, determination of appropriate stimulation levels and electrode placement

- Conduct integrity evaluation of device using telemetry during initial tDCS trial.
- Repeat subset of speech perception assessment before, during and after the initial tDCS application.
- Instructions for completion of electronic daily diary to record adverse events and compliance of auditory training

The tDCS current will be programmed to 2.5mA prior to the start of integrity testing. If 2.5mA is intolerable, then the current will be reduced to 2.0mA. If a participant is still not able to tolerate 2.0mA, then this will be considered a screen fail and the subject will be removed from study.

Study participants meeting the screening criteria upon completion of the baseline visit will continue on study. Enrolled participants will be given a tDCS device to take home to complete study procedures with instructions to return it at the 1 month post-treatment visit to be completed in person.

Weeks 2-5 (Visits 2 – 5)

During the 30-day treatment period, subjects will be expected to complete the following:

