- Complete daily web-based auditory training with tDCS stimulation for 30-minute sessions, at least five times per week for 4 weeks.
- Completion of a daily diary to record compliance of auditory training with tDCS, as well as to document adverse events that may occur during or after the sessions.
- Video visits will be conducted at least weekly by a member of the research team, starting more frequently in the first week, to provide technical assistance as needed, review reported adverse events, and give reminders regarding completion of the daily diary.

One-Month post-treatment (Visit 6)

Participants will be asked to return at the end of the 30-day treatment period for an in-person visit and undergo the following assessments:

- Hearing threshold and speech perception testing using standard audiological procedures (AzBio Quiet, AzBio +5/+10dB; CNC 50-item list)
- Obtain patient reported outcome questionnaires (SSQ-12 and CIQOL)
- Conduct integrity evaluation of device using telemetry
- Review of adverse events
- Return tDCS device

Six-Month post-treatment (Visit 7)

Participants will be asked to return for an in-person visit and undergo the following assessments:

- Hearing threshold and speech perception using standard audiological procedures (AzBio Quiet, AzBio +5/+10dB; CNC 50-item list)

- Obtain patient reported outcome questionnaires (SSQ-12 and CIQOL)
- Conduct integrity evaluation of device using telemetry
- Review of adverse events since the last visit

Schedule of Events Table							
	Baseline	Week 2 (televisit)	Week 3 (televisit)	Week 4 (televisit)	Week 5 (televisit)	1 month post- assessment (in-office visit)	6 month post - assessment (in-office visit)
	Visit 1	Visit 2	Visit 3	Visit 4	Visit 5	Visit 6	Visit 7
Consent	X						
Hearing and Speech Reception Thresholds	X					X	X
Patient Reported Outcome Measures (SSQ12 and CIQOL)	X					X	X
Auditory Training in office – establish therapy plan	X	X					
In-office tDCS – establish protocol, patient training	X						
Home Auditory training and tDCS (daily)					→		
Weekly video visit to review use & compliance of training		X	X	X	X		
Review of symptoms and adverse events		X	X	X	X	X	X
Subject Compensation	X					X	X

6) **Selection of Subjects:**

Inclusion Criteria

1. Age \geq 18 years of age
2. Patients with a unilateral Cochlear Implant device in use for a minimum of 1 year

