tDCS uses low voltage (typically < 20 V) and direct currents (typically < 2 mA) applied through scalp surface electrodes. Thus, it is comparable to connecting a conventional 9 V battery to the electrodes. The low voltages and currents contribute to an excellent safety profile of tDCS. According to a recent review paper (Bikson et al 2016) there are no known long-term health risks from the use of tDCS, *per se*, when operated within consensus safety guidelines. However, minimal, acute side effects of tDCS may include discomfort, skin irritation, lightheadedness, and headache.

- *Potential risk of skin irritation.* The most commonly reported side effect is skin irritation at the sites of the tDCS electrodes. This may include reddening of the skin underneath the electrodes or itching at the site of stimulation. Skin lesions, such as burn-like lesions or contact dermatitis, have also been observed.
- *Potential risk of lightheadedness.* While rare, feelings of pre-syncope, or lightheadedness, with stimulation can occur. This condition can sometimes occur during the “ramp-up” or “ramp-down” phase at the beginning and end of the protocol as the current is changing.
- *Potential risk of headache.* A potential side effect of tDCS is a headache that could develop during or immediately after the stimulation and may last for minutes to hours following the end of the stimulation. It is typically limited to the day of stimulation, and usually responds promptly to single doses of over-the-counter analgesics.
- *Potential risk of impairments in cognitive function.* There has been no evidence of neuronal damage or cognitive impairment induced by tDCS as demonstrated in Nitsche and Paulus (2001) and Nitsche et al. (2003).

As noted above, the primary side effects of tDCS are mostly related to interactions between the electrodes and the scalp skin. These side effects however are mitigated by the proper selection and application of the electrodes. To minimize chemical reactions at the electrode–skin interface, non-metallic, conductive rubber electrodes, covered completely with saline-saturated sponges will be used in this study, as recommended by Nitsche and Paulus, 2000. The electrodes will be single-use and packaged for convenient and safe use at home by the patients.

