It's possible that tDCS pads may cause damage to hearing aid microphones if they get wet. Therefore, participants who wear a contralateral hearing aid will be instructed to remove it prior to and during the use of tDCS.

Participants will record daily symptoms via a link to a REDCap survey. REDCap will be programmed to alert the PI and/or SC of symptoms with an intensity level reported at 8 or above on the AE/symptom survey, regardless of the duration indicated (refer to table below). The PI, SC, or delegate will contact the patient to obtain additional information and determine if tDCS should be discontinued, and if a referral for medical evaluation is needed.

In conclusion, given the low risk of tDCS and its combination with CI, the risk/benefit is favorable since improvement in the patients’ speech perception due to the administration of tDCS could improve their quality of life.

12) Costs to the Subject:

The study does not involve any costs to subjects. Costs for the audiological assessments will be covered by the study. tDCS devices for in-home use will be provided to study participants at no charge and returned at the end of the 1-month follow-up visit.

13) Data Analysis & Statistical Considerations:

The primary outcome measures of feasibility are: 1) proportion of eligible CI patients who expressed interest in the study; 2) proportion of selected participants who completed tDCS training and demonstrated competence in the office and subsequently at home during remote visits; 3) proportion of participants who completed most or all of the proposed intervention protocol; 4) proportion who completed relevant appointments, and reasons for any missing data; 5) acceptability of patient incentive; 6) patient report of ease/difficulty carrying out the protocol via a patient survey at Visit 2; 7) proportion of people with any adverse events, and 8) other feasibility and acceptability metrics consistent with the latest guidelines on pilot studies (Eldridge et al. 2016). After each in-office tDCS application and at the immediate one month post-intervention Visit 6, the site of tDCS stimulation and the CI site will be visually examined for any skin irritation or tenderness and the internal and external CI devices will be examined for signs of abnormal function. Adverse effects of tDCS will be measured by the intensity and duration of symptoms recorded on the daily diary.

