The primary outcome measures of efficacy will be speech perception performance in the best listening condition compared to baseline, progress within the computer-based rehabilitation program and patient report of improved daily communication function. Speech perception performance will be measured using validated and standard word and sentence lists presented in quiet and in noise (AzBio Quiet, AzBio +5/+10dB; CNC 50-item list).

For the primary outcome we are reporting straightforward proportions and will not be conducting any group comparisons. The prevalence with which adverse effects are reported will be determined for the study as a whole and for different time windows during the study. To address efficacy we would compare baseline speech perception and survey results with 1 and 6 month data.

Descriptive analysis will include mean and standard deviations, and may also include evaluate for improvement using paired t-test. Need for statistical consultation is likely to be minimal but will be sought if appropriate.

14) Data & Safety Monitoring:

The PI will ensure proper data and safety monitoring. Any serious adverse events will be reported by the PI to the IRB within 5 business days. Events that are considered both serious and unanticipated will be reported to the IRB within 24 hours of the PI's knowledge of the event. The PI will reconsider study design and procedures in discussion with the IRB should adjustments be warranted.

Adverse events will be monitored from the start of auditory training with tDCS at week 2 until the six-month follow-up visit at visit. The PI and study team will meet frequently to review patient reported adverse events.

The investigator's clinical judgment is used to determine whether a subject is to be removed from treatment due to an adverse event. In the event a subject requests to withdraw from protocol-required therapies or the study due to an adverse event.

Definition of unanticipated and serious adverse events requiring prompt reporting to the IRB are described below:

Unanticipated Problems

The Office for Human Research Protections (OHRP) considers unanticipated problems involving risks to subjects or others to include, in general, any incident, experience, or outcome that meets **all** of the following criteria:

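### No symptom score is taken before the first stimulation, so the diary measure of tDCS adverse effects cannot separate them from pre-existing or background symptoms

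*Combined protocol and SAP*

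**What the plan says.** Section 13 defines the safety measure: "Adverse effects of tDCS will be measured by the intensity and duration of symptoms recorded on the daily diary". It then gives the analysis: "The prevalence with which adverse effects are reported will be determined for the study as a whole and for different time windows". Results are simple proportions without group comparison. This measure has no change from baseline, no relatedness grade and no rule for symptoms that a participant already had.

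Section 5 places the first stimulation at Visit 1: "Repeat subset of speech perception assessment before, during and after the initial tDCS application". The Visit 1 list includes hearing and speech tests, SSQ-12 and CIQOL. For the diary it has only this: "Instructions for completion of electronic daily diary to record adverse events and compliance of auditory training". During the treatment weeks, participants use the diary to "document adverse events that may occur during or after the sessions".

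In the Schedule of Events, the row "Review of symptoms and adverse events" is marked for Visits 2 to 7 and not for Baseline. Section 14 agrees: "Adverse events will be monitored from the start of auditory training with tDCS at week 2 until the six-month follow-up visit".

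Section 11 lists the expected effects: "minimal, acute side effects of tDCS may include discomfort, skin irritation, lightheadedness, and headache".

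**The concern.** Safety is part of the first stated purpose of the study. The speech and questionnaire outcomes have a baseline and are to be compared with it. The symptom outcome does not, although Section 13 labels diary symptoms as effects of tDCS.

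Headache and lightheadedness also occur in people who receive no stimulation. With neither a pre-stimulation reading nor a control arm, the prevalence overall and by time window mixes background with effect. A participant with a habitual headache looks the same as one whose headache began with stimulation. If that habitual headache becomes worse, the diary holds the later intensity but nothing to compare it with. The measure can thus mislead in both directions: it can overstate new symptoms and miss worsening of old ones. With 10 participants planned and at most 14 enrolled, one or two such people visibly move a reported proportion.

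**Working it through.** The documents state no adverse event rate, so there is no figure of the plan's own to reproduce. The check is first one of timing, then an illustration.

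**Timing**

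1. First exposure: Visit 1, in the office (Section 5).
2. Diary at Visit 1: instructions only (Section 5).
3. Symptom review: Visits 2 to 7, not Baseline (Schedule of Events).
4. Adverse event questionnaire: during the four weeks of training (Section 4).
5. Start of adverse event monitoring: week 2 (Section 14).
6. Examination of the stimulation and CI sites: after in-office stimulation and at Visit 6 (Section 13). No examination before stimulation is described.
7. Baseline questionnaires: SSQ-12 and CIQOL, which concern hearing and CI quality of life and do not score the tDCS symptom list.

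Every scheduled symptom reading therefore falls after first exposure, and the separate places agree.

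**Illustration of size**

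Inputs from the documents: five or more sessions a week for four weeks, so at least 5 × 4 = 20 entries per participant; 4 × 7 = 28 if the diary is completed every day. Assumed inputs: a background chance q that any one entry contains a symptom, the same for all participants, with independent entries and no tDCS effect. The share of participants with at least one symptom in s entries is 1 − (1 − q)^s.

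| Assumed q per entry | 20 entries | Expected number of 10, at 20 entries | 28 entries |
|---|---|---|---|
| 0.5% | 9.5% | 1.0 | 13.1% |
| 1% | 18.2% | 1.8 | 24.5% |
| 2% | 33.2% | 3.3 | 43.2% |
| 5% | 64.2% | 6.4 | 76.2% |
| 10% | 87.8% | 8.8 | 94.8% |

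For example, at q = 2%: 1 − 0.98^20 = 0.332.

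**What one baseline reading can and cannot do**

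Under the same model, suppose the Visit 1 reading recalls the past 7 days. A participant is symptom-free at that reading with probability (1 − q)^7 and still records a background symptom later with probability 1 − (1 − q)^20. The share wrongly shown as having a new symptom is the product:

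- q = 2%: 0.868 × 0.332 = 0.29
- q = 5%: 0.698 × 0.642 = 0.45
- q = 10%: 0.478 × 0.878 = 0.42

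The corresponding shares without any baseline reading are 33%, 64% and 88%. A single reading thus leaves much of the sporadic background. This model has no habitual sufferers in it, and they are the group that a single reading identifies best.

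**The case against.** The strongest reply has five parts.

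- **Session link.** The diary covers events during or after sessions, and weekly video visits review the entries. This stands in part. However, no time limit is set on what counts as after a session, so a habitual headache later that day still qualifies. The weekly review, and the contact triggered at intensity 8 or above, serve safety management; nothing carries those judgements into the Section 13 measure.
- **Unseen instrument.** The survey table to which Section 11 refers is not in the text available here, so an item on relatedness cannot be excluded. This stands. Such an item would help attribution but would not supply a pre-stimulation score.
- **Local symptoms.** Skin irritation and itching at the electrode site are hard to mistake for background. This stands, and it confines the point mainly to headache and lightheadedness.
- **Assumed rates.** The percentages rest wholly on q and on independence. This stands. If symptoms cluster in a few people, the share ever affected is lower at the same average rate. The formula also counts any symptom, whereas the criticised sentence concerns intensity and duration.
- **Conservative convention.** Reporting every symptom whatever its cause overstates harm rather than hiding it. That is fair for the count of symptoms, but it does not help to recognise worsening of an existing one.

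A reader might infer that existing symptoms are definitely counted as tDCS effects, or that most of the reported prevalence will be background. The documents support neither: the full survey is not visible and no background rate is given. Nor does the point extend fully to the primary outcome of any adverse event, which Section 13 does not attribute to tDCS.

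**Conclusion.** The point holds in a limited form. The absence of a scheduled symptom score before first stimulation is clear from the Visit 1 list, the Schedule of Events and the start of monitoring in Section 14. With no control arm and no attribution rule in the analysis, the diary measure cannot separate tDCS effects from pre-existing or habitual symptoms, chiefly the non-local ones, and cannot show worsening.

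The size and net direction of the bias cannot be determined from the documents. The range of about 10% to 88% illustrates how far background alone could reach under assumed, independent rates of 0.5% to 10% per entry over 20 entries; it is not an estimate for this study. This is a worthwhile, inexpensive improvement to an uncontrolled pilot, not an error that invalidates its safety reporting.

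**What to change.** - **Visit 1 (Section 5 and Schedule of Events):** have each participant complete the existing REDCap symptom survey once before any current is applied, with a stated recall period such as the past week.
- **Section 13:** report symptoms that are new or worsened against that reading, beside all reported symptoms. State that a single recall reading identifies habitual symptoms but does not remove sporadic background, and that a recall score is not directly equivalent to a daily entry.
- **Diary days:** Section 5 ties diary events to sessions, while Section 11 describes daily symptom recording. Reconcile the two. If the diary is completed on days without a session (28 − 20 = 8 days at five sessions a week), also tabulate symptoms by session and non-session day as an internal reference.

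The cost is a few minutes at Visit 1, reliance on recall, and one added table. The reading cannot be recovered later for anyone already stimulated.

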**Safety and Feasibility of Transcranial Direct Current Stimulation to Enhance Auditory
Rehabilitation in Cochlear Implant Recipients**

Document Date: 11/09/2022

NCT04908631

**Safety and Feasibility of Transcranial Direct Current Stimulation to Enhance
Auditory Rehabilitation in Cochlear Implant Recipients**

Sponsor:	PI – Department of Head and Neck Surgery & Communication Sciences
Funding Source:	MEDx
Protocol Source:	PI – Department of Head and Neck Surgery & Communication Sciences
Duke IRB#:	Pro00107525
IND#:	N/A
Principal Investigator [name], MBA, FACS Department of Head and Neck Surgery & Communication Sciences [REDACTED]	Study Coordinator [name] HNSCS [REDACTED]
Sub Investigator(s) [name] [REDACTED]	[name] HNSCS [REDACTED]
[name], AuD, PhD [REDACTED]	[name] Brain Stimulation and Neurophysiology [REDACTED]
[name], AuD, CCC-A [REDACTED]	Regulatory Coordinator [name] [REDACTED]
[name] [REDACTED]	Data Manager [name] [REDACTED]
See IRB submission for a detailed list of study personnel.	
Version date:	11/9/2022

1) **Protocol Title:** Safety and Feasibility of Transcranial Direct Current Stimulation to Enhance Auditory Rehabilitation in Cochlear Implant Recipients

2) **Purpose of the Study:**

- a) To evaluate the safety and feasibility of reliable Transcranial Direct Current Stimulation (tDCS) administration at home in combination with home-based auditory training therapy and practice in Cochlear Implant (CI) patients
- b) To evaluate changes in speech perception performance after a 4-week intervention consisting of tDCS combined with auditory rehabilitation and training.

3) **Background & Significance:**

[figure not shown]

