3. Sentence recognition scores (AzBio) are below 65% in quiet and/or word recognition scores (CNC) are below 75% in the implanted ear for \geq one year following cochlear implant activation.
4. Ability to access internet to conduct computer-based auditory trainings and weekly video visits with study team weeks 2–5

Exclusion Criteria

1. Non-English speaking
2. Diagnosis (documented or self-reported) of a psychiatric or neurologic condition, or any other comorbidities that may interfere with the study or increase the level of risk (such as dementia, seizures, legal blindness, brain tumor)
3. Implants, other than CI, above collar bone level that may interact with delivery of tDCS
4. Inability to or unwillingness to use electronic devices/computers, participate in video visits, or make required visits

7) **Subject Recruitment and Compensation:**

10 patients from the Duke Head and Neck and Communication Science clinics and/or the Duke Raleigh HNSCS Clinic will be recruited. Patients who meet the inclusion and exclusion criteria listed above will be approached for possible study participation after a member of the clinical care team asks the patient's permission to be contacted by the study team. The study coordinator (or member of the research team) will then review the records, and upon determination that the patient is deemed eligible for this protocol, the clinical research coordinator (CRC) will contact the patient. This may occur in clinic or via phone using an IRB approved phone script. If the patient indicates interest in study participation, the study coordinator will thoroughly explain the required elements of informed consent and all aspects of the study to the subject including inclusion/exclusion criteria, risks, benefits, and alternative to study participation. Up to 14 patients will be enrolled, allowing for 4 drop-outs.

Subjects will be compensated \$75 upon completion of the baseline visit (visit 1), \$100 upon completion of the one-month f/u visit (visit 6) and \$75 upon completion of the six-month follow up visit (visit 7) for total of \$250.

8) **Consent Process:**

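### The primary proportions are planned with no measure of precision, although at 10 to 14 participants their exact 95% limits are very wide

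*Combined protocol and SAP*

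**What the plan says.** Section 2 gives the first purpose as "To evaluate the safety and feasibility of reliable Transcranial Direct Current Stimulation (tDCS) administration at home", in combination with auditory training in cochlear implant patients. The title puts the same two aims first.

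Section 7 sets the size: "10 patients from the Duke Head and Neck and Communication Science clinics and/or the Duke Raleigh HNSCS Clinic will be recruited". It then adds: "Up to 14 patients will be enrolled, allowing for 4 drop-outs". No reason is given for either number.

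Section 13 (Data Analysis & Statistical Considerations) lists eight primary feasibility measures. Two that matter here are "3) proportion of participants who completed most or all of the proposed intervention protocol" and "7) proportion of people with any adverse events". The analysis is then stated: "For the primary outcome we are reporting straightforward proportions and will not be conducting any group comparisons". The section also plans the prevalence of adverse effects, overall and by time window. For other summaries it says: "Descriptive analysis will include mean and standard deviations, and may also include evaluate for improvement using paired t-test". It expects little need for statistical advice, but says advice will be obtained where warranted.

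No section gives an interval for any proportion, an acceptable adverse-event rate, a feasibility threshold, or a denominator for the safety proportion.

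**The concern.** Safety and feasibility are the questions the trial exists to answer, and the plan answers them with point proportions from about ten people. A proportion from so few carries little information by itself, and the plan offers neither a statement of precision nor a criterion that would tell a reader how much weight it can bear.

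The safety side deserves the most care. Section 11 describes the pairing of tDCS with a cochlear implant as novel and supports its safety with simulations, a manufacturer's testing and reports of another implanted stimulator. This trial supplies direct patient data on the combination, so the precision of those data bounds what can be concluded.

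**Working it through.** **Inputs.** n = 10 and n = 14, both from Section 7. The documents give no confidence level or type of interval; I assume two-sided 95% exact (Clopper-Pearson) limits and show one-sided limits as the range. Each participant is taken as one independent binomial observation.

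**The plan's own figure.** 10 + 4 = 14, so the enrolment ceiling follows from the drop-out allowance (4/14 = 28.6%). The 10 itself cannot be reproduced, because no power, precision or expected rate is stated.

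**Formulas.** For x events in n, the lower limit is the 0.025 quantile of Beta(x, n − x + 1) and the upper limit is the 0.975 quantile of Beta(x + 1, n − x). For x = 0 the lower limit is 0 and the upper limit is 1 − 0.025^(1/n). For x = n the upper limit is 1 and the lower limit is 0.025^(1/n).

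**Zero counts.**
- n = 10: 1 − 0.025^(1/10) = 1 − 0.692 = 30.8%. One-sided 95%: 1 − 0.05^(1/10) = 25.9%.
- n = 14: 1 − 0.025^(1/14) = 1 − 0.768 = 23.2%. One-sided 95%: 1 − 0.05^(1/14) = 19.3%.

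Across these choices the upper limit runs from about 19% to 31%.

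**Other possible results, two-sided 95%.**

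| Result | Point estimate | Exact limits |
|---|---|---|
| 1/10 | 10% | 0.3% to 44.5% |
| 8/10 | 80% | 44.4% to 97.5% |
| 10/10 | 100% | 69.2% to 100% |
| 10/14 | 71.4% | 41.9% to 91.6% |

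The last row is the completion result if all 14 are enrolled and all four allowed drop-outs occur. Neither 8/10 nor 10/14 excludes a true completion rate below one half.

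**How often a real risk would go unseen.** The chance of no events is (1 − p)^n.

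| True risk p | n = 10 | n = 14 |
|---|---|---|
| 5% | 59.9% | 48.8% |
| 10% | 34.9% | 22.9% |
| 20% | 10.7% | 4.4% |

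**Which denominator.** The plan does not say. Section 5 gives a first tDCS application in the office at baseline and treats those who cannot tolerate the lower current as screen failures, so some people may be exposed and then not counted. Section 14 starts adverse-event monitoring at week 2, after that application. Section 13, however, has the skin and the implant examined after each in-office application. The safety denominator could therefore be 10, 14 or another number.

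**The case against.** The strongest reply is that this is a single-arm pilot, that descriptive reporting suits it, and that anyone given x and n can work out the limits. The first part stands: the absence of group comparisons is no fault, and no hypothesis test is being asked for. The second part holds only if the denominator is clear, which for safety it is not. An interval is itself descriptive.

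Several stronger readings are tempting, and the documents do not support them.

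- *That 0/10 would be declared safe.* No sentence says so, and no decision rule exists. Section 11 does cite an earlier series of more than 69 healthy subjects without adverse events as reassurance, with no interval, but that is a remark about past work and not a planned conclusion.
- *That the plan excludes intervals.* The Section 13 sentence rules out group comparisons and is silent on precision. The remark on statistical advice does not settle the matter either, since it leaves room to seek help.
- *That zero is a likely result for the listed safety measure.* That measure counts any adverse event. Sections 10 and 11 of the protocol's risk discussion aside, the documents give no rate, but Section 11 names skin irritation and similar minor symptoms as the most common effects, and participants complete at least 5 × 4 = 20 sessions with a daily diary. If the true rate were 30%, 0/10 would have probability 0.7^10 = 2.8%; at 50% it would be 0.1%. Both rates are assumptions. The zero-count figures matter for serious or implant-related events.
- *That every primary result is a proportion of about 10.* Item 1 is based on eligible patients, and items 5 and 6 are not stated as proportions.
- *That safety rests on one proportion.* The plan also records symptom intensity and duration, inspects the skin and implant site, checks implant function and runs telemetry. These add evidence, but none supplies an interval.

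Item 8 points to guidance on pilot studies, but for further metrics, not for how the proportions are analysed.

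**Conclusion.** The point holds as a gap in precision, not as a planned misinterpretation. The primary proportions are to be reported with no interval and no criterion, from 10 to 14 people. Eight completers out of 10 would leave the true rate anywhere from 44.4% to 97.5%. A zero count of serious or implant-related events would leave a true risk of up to 30.8% (n = 10) or 23.2% (n = 14) unexcluded.

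These figures rest on two-sided 95% exact limits and on denominators of 10 or 14. One-sided limits bring the zero-count bounds down to 25.9% and 19.3%, which does not change the conclusion. The omission biases no estimate and affects no data collected. It concerns how much the title question can be said to have been answered, and it should be corrected before results are reported.

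**What to change.** Replace the Section 13 sentence on the primary analysis with:

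> Each primary outcome that is a proportion will be reported as numerator/denominator with an exact (Clopper-Pearson) two-sided 95% confidence interval, without group comparisons. The safety denominator is every participant who received any tDCS, including the in-office application. Intervals will be given separately for any adverse event and for serious or CI-related events, and conclusions on safety and feasibility will cite these limits.

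Here CI means cochlear implant, as in the protocol. Keeping the two event classes apart stops minor skin symptoms from driving the safety statement by themselves.

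One consequence needs attention: if the denominator includes the in-office application, events from it must be in the numerator too, so the monitoring start in Section 14 has to be reconciled with this definition.

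The computation is trivial, and the design and sample size do not change. The price is that the conclusions will be more modest.
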